Data Cleaning Plan **DCP** deoxyribonucleic acid **DNA**

Data Monitoring Committee DMC

electrocardiogram **ECG**

EDC electronic data capture

European Medicines Agency **EMA eCRF** electronic Case Report form

ES **Enrolled Set EOS** End of Study

Full Analysis Set

FcRn neonatal Fc receptor for IgG

GCP Good Clinical Practice

GMP Good Manufacturing Practice

glycosylated hemoglobin HbA1c

HIV human immunodeficiency virus

HLA

ICH

IEC

Ig

Jard
Jocytopenia
Jocytope **IGRA IMP INR**

IRB **ITP**

ITP-BAT

iv

IVIg

IXRS

LTB

LLOQ

LP

MCID

Medical Dictionary for Regulatory Activities MedDRA

major histocompatibility complex **MHC**

magnetic resonance imaging MRI mRNA messenger ribonucleic acid

micro ribonucleic acid miRNA

Neurological Fatigue Index for Multiple Sclerosis **NFI-MS**

NTMBI nontuberculosis myobacterial infection

no observed adverse effect level

pharmacodynamic(s)

his do childen RDILI potential drug-induced liver injury Pharmacodynamic Per Protocol Set

peak expiratory flow PK pharmacokinetic(s)

PK-PPS Pharmacokinetic Per Protocol Set

PLEX plasma exchange **PPS** Per Protocol Set

PRO Patient Reported Outcome

PS Patient Safety

PTT partial thromboplastin time

corrected QT interval QTc

RNA ribonucleic acid

SAE serious adverse event

SAP Statistical Analysis Plan

scsubcutaneous

SD standard deviation

tion and any extensions or warrations thereof. skin (S), visible mucosae (M), and organs (O), with gradation of severity **SMOG**

SOP

SS

treatment-emergent adverse event thrombopoietin-receptor apper limit of norm alosis

atment-emergen

thrombopoietin-recei

upper limit of normal

SUMMARY

Primary immune thrombocytopenia (ITP) is a disease which is characterized by an isolated low platelet count (thrombocytopenia) and the absence of other causes of thrombocytopenia. It is an autoimmune disease which is characterized by specific autoantibodies directed against platelets. There is no causal treatment. Treatment options include immunosuppressive therapy, immunoglobulin therapy, and splenectomy. There is an unmet medical need for new treatment options due to significant side effects, significant risks, and significant complexity of existing therapy.

The neonatal major histocompatibility complex (MHC)-class-I-like neonatal Fc receptor for IgG (FcRn) binds immunoglobulin G (IgG), thereby preventing IgG from intracellular lysosomal degradation. UCB7665 is a humanized IgG4 monoclonal antibody that has been specifically designed to inhibit IgG binding to FcRn with the aim to reduce the concentration of pathogenic IgG in patients with IgG autoantibody mediated diseases, including ITP. Thereby, it represents a potential new mode of action to target the underlying pathomechanism of ITP and could enhance the still limited treatment options.

TP0001 is a Phase 2, multicenter, open-label, multiple-dose, multiple-arm study to evaluate the safety, tolerability, and efficacy of UCB7665 administered as subcutaneous (sc) doses of 4mg/kg, 7mg/kg, 10mg/kg, 15mg/kg, and 20mg/kg (resulting in cumulative doses of 20mg/kg, 21mg/kg, 20mg/kg, 15 mg/kg and 20mg/kg respectively), in subjects ≥18 years of age with persistent (>3 months up to 12 months after diagnosis) or chronic (more than 12 months after diagnosis) primary ITP.

The study is planned to be conducted at up to approximately 45 sites in Europe and Australia. A total of approximately 48 to 66 subjects (dependent on emerging safety data and corresponding DMC recommendation) are planned to enter the Dosing Period in the study. The maximum study duration for study participation for an individual subject is approximately 16 weeks.

The study is intended to evaluate 5 dose arms of UCB7665. Subjects in Dose Arm 1 will receive 5 doses of UCB7665 4mg/kg sc at 1 week intervals, subjects in Dose Arm 2 will receive 3 doses of UCB7665 7mg/kg sc at 1 week intervals, subjects in Dose Arm 3 will receive 2 doses of UCB7665 10mg/kg sc at 1 week intervals, Dose Arm 4 will receive 1 dose of UCB7665 15mg/kg sc and Dose Arm 5 will receive 1 dose of UCB7665 20mg/kg sc.

The study consists of a Screening Period (up to 4 weeks), Dosing Period of 1 day to 4 weeks where dosing arms are introduced sequentially, and an Observation Period of 8 weeks. The Screening Visit corresponds to Visit 1 of the study. The Dosing Period will commence at Visit 2 (Baseline Visit), with dosing visits scheduled at weekly intervals for Dose Arms 1, 2 and 3 and only one visit scheduled for Dose Arms 4 and 5. The Observation Period will start after the last dose administration (or only dose administration for Dose Arms 4 and 5) with a visit scheduled 3 Period, ie, 8 weeks after the last or only dose of investigational medicinal product (IMP).

The first 6 subjects will be enrolled in Dose Arm 1 only While data for the first 3 subjects. days after the last dosing and weekly visits thereafter (ie, weekly after last or only dose) for a period of 8 weeks. The End-of-Study Visit will be performed at the end of the Observation

The first 6 subjects will be enrolled in Dose Arm 1 only. While recruitment is ongoing, safety data for the first 3 subjects up to 7 days after the last dose of the third subject will be reviewed by the Data Monitoring Committee (DMC). During a second DMC meeting, all available safety data up to cut off date defined as 7 days after the last dose of the sixth subject will be reviewed.

Following this review, the DMC will make a recommendation on whether to open Dose Arm 2 for enrollment. Once the DMC has advocated the initiation of Dose Arm 2, the subsequent subjects for the first 2 arms will be randomly assigned in 1:1 ratio to either Dose Arm 1 or Dose Arm 2 using an interactive voice/web response system (IXRS). Once 15 subjects are enrolled in Dose Arm 1, the subsequently enrolled subjects will be enrolled in Dose Arm 2.

After the safety data review of at least 6 subjects in Dose Arm 2 is done, the DMC will make a recommendation on whether to open Dose Arm 3 for enrollment. Once the DMC has advocated the initiation of Dose Arm 3 and the enrollment of 15 subjects into Dose Arm 2 has been completed, the subsequent subjects will be assigned to Dose Arm 3 only. After every third subject has been enrolled, DMC will review all available safety data up to cut off date defined as 7 days after the last dose of the respective subject. Depending on the emerging safety data of 6 subjects in Dose Arm 3, the DMC will recommend whether to open Dose Arm 4 for enrollment or to include additional subjects in Dose Arm 3. If applicable, this procedure is planned to be repeated stepwise in groups of 3 subjects. A maximum of 12 subjects are planned for Dose Arm 3. The DMC will recommend to open Dose Arm 4 for enrollment in a subsequent DMC meeting, if applicable.

Once the DMC has advocated the initiation of Dose Arm 4, the enrollment of Dose Arm 3 will be closed and all subsequently enrolled subjects will be assigned to Dose Arm 4. After every third subject that has been enrolled, DMC will review all available safety data up to cut off date defined as 7 days after the last dose of the respective subject. Depending on the emerging safety data of 6 subjects in Dose Arm 4, the DMC will recommend whether to open Dose Arm 5 for enrollment or to include additional subjects in Dose Arm 4. If applicable, this procedure is planned to be repeated stepwise in groups of 3 subjects. A maximum of 12 subjects are planned for Dose Arm 4. The DMC will recommend to open Dose Arm 5 for enrollment in a subsequent meeting, if applicable.

Once the DMC has advocated the initiation of Dose Arm 5, the enrollment of Dose Arm 4 will be closed and the subsequently enrolled subjects will be assigned to Dose Arm 5. After every third subject is enrolled, the DMC will review all available safety data up to the cutoff date defined as 7 days after the dosing of the third subject in Dose Arm 4. Depending on the emerging safety data of 6 subjects in Dose Arm 5, the DMC will recommend to include additional subjects in Dose Arm 5. If applicable, this procedure is planned to be done stepwise in groups of 3 subjects. A maximum of 12 subjects may be enrolled in Dose Arm 5.

The DMC may also decide to reduce the number of doses dose arms, to stop a dose arm or not to open a dose arm based on review of safety data during the study. Safety data will also be reviewed on an ongoing basis by clinical research organization (CRO) medical monitor and UCB physician during the study so as to continuously evaluate the safety of subjects.

The primary objective of the study is to evaluate the safety and tolerability of UCB7665 administered by sc infusion in subjects with ITP.

The secondary objective of the study is to assess the clinical efficacy of UCB7665 as measured by the change in platelet count and to assess the pharmacodynamic (PD) effect of UCB7665 as measured by the change in total IgG concentrations in serum. The exploratory objectives include the following:

to evaluate the clinical efficacy as measured by

the change in ITP bleeding score; to evaluate the effect of UCB7665 on the concentrations of total protein, albumin, α-globulin and β-globulin, IgG subclasses, IgM, IgA, and IgE, and serum and plasma complement levels; to evaluate the emergence of anti-drug antibodies (ADA), ie,

The primary safety variable is the occurrence of treatment-emergent adverse events (TEAEs). Other safety variables are TEAEs leading to withdrawal of IMP, vital signs, 12-lead electrocardiogram (ECG), laboratory parameters (hematology including coamilations of the company of

Other safety assessments are evaluation of potential drug-induced liver injury (PDILI), using pre-specified criteria for managing any PDILI events in accordance with the Drug Administration (FDA) Guidance for Industry, Drug-Induced Liver Injury, Premarketing Clinical Evaluation (Jul 2009).

The following efficacy variables will be assessed: Response (platelet count >30x10⁹/L and at least 2-fold increase of the Baseline count) during the study and by visit; Complete Response (platelet count $\ge 100 \times 10^9 / L$) during the study and by visit; platelet count $\ge 50 \times 10^9 / L$ during the study and by visit; the maximum value and maximum increase from Baseline in platelet count during the study; value and change from Baseline in platelet count over time; Baseline-corrected area under the effect curve (AUEC) for platelet count, time to Response (time from starting treatment to achievement of Response); time to Complete Response (time from starting treatment to achievement of Complete Response); time to achieving platelet count >50x10⁹/L; duration of Response (measured from achievement of Response to loss of Response [defined as platelet count below $30x10^9/L$ or less than 2-fold increase of Baseline platelet count]); duration of Complete Response (measured from achievement of Complete Response to loss of Complete Response [defined as platelet count below $100 \times 10^9 / L$]); duration of platelet count $\geq 50 \times 10^9 / L$ (measured from achievement of platelet count $\geq 50 \times 10^9 / L$ to reduction of platelet count below 50×10^9 /L); Clinical Response (defined as platelet count $\geq 30 \times 10^9$ /L and at least 2-fold increase from Baseline value and absence of bleeding); time to Clinical Response (time from starting treatment to achievement of Clinical Response); duration of Clinical Response (measured from achievement of Clinical Response to loss of Clinical Response [loss of Clinical Response defined as platelet count $<30 \times 10^9/L$ or less than 2-fold increase from Baseline platelet count or presence of bleeding]); Complete Clinical Response (defined as platelet count $\geq 100 \times 10^9 / L$ and absence of bleeding); time to Complete Clinical Response (time from starting treatment to achievement of Complete Clinical Response); duration of Complete Clinical Response (measured from achievement of Complete Clinical Response to loss of Complete Clinical Response [loss of Complete Clinical Response defined as platelet count <100x10⁹/L or presence of bleeding]); no Clinical Response (defined as platelet count <30x10⁹/L and less than 2-fold increase from Baseline or presence of bleeding); ITP bleeding score over time; and Patient Reported Outcome (PRO), ie, Neurological Fatigue Index for Multiple Sclerosis (NFI-MS) summary score over time. Plasma concentration of UCB7665 over time will be assessed as the PK variable. The PD variables are minimum value and maximum decrease in total IgG concentration during the study; IgG subclass concentrations; and ITP-specific autoantibody

in serum over time. Other immunological variables to be evaluated are total IgA, IgE, and IgM levels; serum (C3 and C4) and plasma (C3a and C5a) complement levels; ADA status (negative/positive) and relative mass units; exploratory safety

and B cell activating and B cell activating and B cell activating infusion.

During this study, subjects will also have the option of providing additional informed consent for exploratory deoxyribonucleic acid (DNA) and ribonucleic acid (RNA) (ie, messenger RNA [mRNA] and micro RNA [miRNA]) analyses. Participation in this additional genomic same! in this exploratory genomic substudy.

Prior to this amendment, a protocol amendment 2 with a dose arm 4mg/kg twice weekly was planned, however the corresponding protocol amendment 2 was not implemented. These changes are highlighted in Section 18.8.

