5 STUDY DESIGN

5.1 Study description

This is a Phase 2, multicenter, open-label, multiple-dose, multiple-arm study to evaluate the safety, tolerability, and efficacy of UCB7665 in subjects with primary persistent or chronic ITP.

Dose Arm 1 (15 subjects): UCB7665 4mg/kg sc (5 doses at an interval of 1 week)

Dose Arm 2 (15 subjects): UCB7665 7mg/kg sc (3 doses at an interval of 1 week)

Dose Arm 3 (6 to 12 subjects): UCB7665 10mg/kg sc (2 doses at an interval of 1 week)

Dose Arm 4 (6 to 12 subjects): UCB7665 15mg/kg sc (1 dose)

Dose Arm 5 (6 to 12 subjects): UCB7665 20mg/kg sc (1 dose)

The maximum duration of the study per subject is approximately 16 weeks, consisting of a Screening Period (1 to 28 days), a Dosing Period of 1 to 4 weeks, and an Observation Period of 8 weeks.

Screening Period: The purpose of the Screening Period is to evaluate and confirm the subject's eligibility. During the Screening Visit (Visit 1), subjects will sign a written Informed Consent

Confidential Page 23 of 353

15 Feb 2017 TP0001

form prior to the conduct of any study-related procedures. The use of concomitant medication while in the study will be discussed, and the subject's eligibility will be determined on the basis of the inclusion/exclusion criteria. The Screening Period should not exceed 28 days.

Dosing Period: The first 6 subjects in the study will receive UCB7665 4mg/kg. These subjects in the Dose Arm 1 will not be randomized. While recruitment is still ongoing, safety data for the first 3 subjects up to 7 days after the last dose of the third subject in Dose Arm 1 will be reviewed by the DMC. During a second DMC meeting, all available safety data up to cut off date defined as 7 days after the last dose of the sixth subject in Dose Arm 1 will be reviewed. During these reviews recruitment in the dose arm will not be stopped. Following this review, the DMC will make a decision on whether to open Dose Arm 2 for enrollment. Once DMC has advocated the initiation of Dose Arm 2, the subsequent subjects will be randomly assigned in 1:1 ratio to either Dose Arm 1 or Dose Arm 2 using an IXRS. Once 15 subjects are enrolled in the Dose Arm 1, the remaining subjects will be enrolled in Dose Arm 2.

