After the safety data review of at least 6 subjects in Dose Arm 2 is done, the DMC will make a recommendation on whether to open Dose Arm 3 for enrollment. Once the DMC has advocated the initiation of Dose Arm 3 and the enrollment of 15 subjects in Dose Arm 2 has been completed, the subsequent subjects will be assigned to Dose Arm 3 only. After every third subject has been enrolled, the DMC will review all available safety data up to cut off date defined as 7 days after the dosing. Depending on the emerging safety data of 6 subjects in Dose Arm 3, the DMC will recommend whether to open Dose Arm 4 for enrollment or to include additional subjects in Dose Arm 3. If applicable, this step is planned to be done stepwise in groups of 3 subjects. A maximum, 12 subjects will be enrolled in Dose Arm 3. The DMC will recommend to open Dose Arm 4 for enrollment in a subsequent DMC meeting, if applicable.

Once the DMC has advocated the initiation of Dose Arm 4, the enrollment of Dose Arm 3 will be closed and all subsequent subjects will be assigned to Dose Arm 4. After every third subject is enrolled, the DMC will review all available safety data up to the cutoff date defined as 7 days after the dosing. Depending on the emerging safety data of 6 subjects in Dose Arm 4, the DMC will recommend to include additional subjects in Dose Arm 4 or not. If applicable, this step is planned to be done stepwise in groups of 3 subjects. A maximum of 12 subjects may be enrolled in Dose Arm 4. The DMC will recommend to open Dose Arm 5 for enrollment in a subsequent meeting, if applicable.

Once the DMC has advocated the initiation of Dose Arm 5, the enrollment of Dose Arm 4 will be closed and all subsequent subjects will be assigned to Dose Arm 5. After every third subject is enrolled, the DMC will review all available safety data up to the cutoff date defined as 7 days after the dosing. Depending on the emerging safety data of 6 subjects in Dose Arm 5, the DMC will recommend to include additional subjects in Dose Arm 5. If applicable, this step is planned to be done stepwise in groups of 3 subjects. A maximum of 12 subjects may be enrolled in Dose Arm 5.

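### The Protocol Summary ties the Dose Arm 5 DMC data cut-off to a Dose Arm 4 subject, a date before any 20mg/kg dose is given

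*Protocol*

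**What the plan says.** The protocol states the DMC cut-offs for Dose Arms 3 to 5 in two places: Section 1 (Summary) and Section 5.1 (Study description).

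- **Summary, Dose Arms 3 and 4.** After every third subject the DMC reviews the data "up to cut off date defined as 7 days after the last dose of the respective subject".
- **Summary, opening of Dose Arm 5.** "safety data of 6 subjects in Dose Arm 4, the DMC will recommend whether to open Dose Arm 5" or add subjects to Arm 4. Once Arm 5 is advocated, Arm 4 enrollment closes and later subjects go to Arm 5.
- **Summary, Dose Arm 5.** After every third subject the DMC reviews data "up to the cutoff date defined as 7 days after the dosing of the third subject in Dose Arm 4". The next sentence reads: "Depending on the emerging safety data of 6 subjects in Dose Arm 5, the DMC will recommend to include additional subjects". Expansion is in steps of three, to at most 12.
- **Section 5.1, Dose Arms 4 and 5.** The DMC reviews "all available safety data up to the cutoff date defined as 7 days after the dosing". No other arm is named.
- **Section 5.1, design list.** "Dose Arm 5 (6 to 12 subjects): UCB7665 20mg/kg sc (1 dose"; each Arm 5 subject is therefore dosed once.

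Section 14.7 says that data are reviewed after every three subjects in Arms 3 to 5. It gives no cut-off for these arms and refers to the DMC charter. Section 12.1.9 refers back to Section 5.1.

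**The concern.** A review cut-off has to lie after the exposure under review. The Summary's cut-off for Arm 5 belongs to the preceding arm, at a lower dose (15mg/kg), and to a subject dosed before Arm 5 could open. It is also a single calendar date, whereas the cut-offs for Arms 3 and 4 move forward with each group of three.

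The Arm 5 reviews are the DMC's scheduled look at the highest single dose in the study, and safety is the primary objective. Anyone who prepares the data snapshot or checks DMC conduct against the Summary has a rule that cannot be followed. No other place in the protocol gives an explicit cut-off that names the Arm 5 subject.

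**Working it through.** No sample size, power or alpha is involved. The check is one of date order and of consistency between the two places.

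**Inputs**
- Arm 4: one dose per subject; six subjects reviewed before Arm 5 can open (Summary, Section 5.1).
- Arm 5: one dose per subject, 6 to 12 subjects, review after every third (Summary, Section 5.1).
- Arms 1 and 2: 15 subjects each; Arms 3 to 5: 6 to 12 each (Section 5.1).

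**Arm sizes against the planned total.** 15 + 15 + 3 × 6 = 48 and 15 + 15 + 3 × 12 = 66. This matches the stated range of 48 to 66, so the arm sizes are read correctly.

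**Date order.** Let a₃ and a₆ be the dosing days of the third and sixth Arm 4 subjects, D the day of the DMC review that may open Arm 5, and b₁ the day of the first Arm 5 dose.
- Summary cut-off for Arm 5: C = a₃ + 7.
- The review of six Arm 4 subjects uses data to a₆ + 7, so D ≥ a₆ + 7.
- Arm 5 subjects are assigned only after that review, so b₁ > D.
- Since a₃ ≤ a₆: C = a₃ + 7 ≤ a₆ + 7 ≤ D < b₁.

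The cut-off precedes the first 20mg/kg dose at any rate of recruitment. A simulation of 100,000 random Arm 4 dosing sequences found no exception, as the inequality requires.

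**Number of reviews affected.** 6 / 3 = 2 to 12 / 3 = 4 reviews. C does not move between them, so the number of Arm 5 subjects with any post-dose data inside the literal cut-off is 0 at each.

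**The statements side by side**

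| Place | Arm | Cut-off: 7 days after … |
|---|---|---|
| Summary | 3 and 4 | last dose of the respective subject |
| Summary | 5 | dosing of the third Arm 4 subject |
| Section 5.1 | 4 and 5 | the dosing (subject not named, no other arm named) |
| Section 14.7 | 3 to 5 | no cut-off given; DMC charter |

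Only the Summary's Arm 5 entry points to another arm. It also conflicts with the sentence after it, which bases the recommendation on six Arm 5 subjects.

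**With the fix.** The cut-offs become b₃ + 7, b₆ + 7, b₉ + 7 and b₁₂ + 7, where b₃ is the dosing day of the third Arm 5 subject and so on. Each is Day 8 of the respective Arm 5 subject.

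**The case against.** The strongest reply is that this is a drafting slip in a synopsis which no DMC would follow. Much of that stands. The next sentence calls for data on six Arm 5 subjects, Section 5.1 has no Arm 4 anchor, and Section 14.7 says the interim analyses cover the charter-specified safety data available at the time. The amendment record in Section 18.9 shows a parallel slip for Arm 4, anchored there to Arm 3. The current Summary reads correctly for Arm 4, so the Arm 5 sentence was probably missed in the same correction. The finding does not depend on that history: the wrong arm stands in the current text.

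Four stronger readings are tempting, and the documents do not support them.

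- **That the 20mg/kg arm would in practice be expanded without 20mg/kg data.** The Summary's next sentence rules this out. The sponsor's and CRO's ongoing medical review, immediate reporting of serious events and events of interest (Section 12.5), and ad hoc DMC meetings (Section 14.7) also stand in the way.
- **That all two to four reviews decide on adding subjects.** The stated decision starts with six subjects, and the cap is 12. No expansion decision is stated at the third subject, and none is possible at the twelfth.
- **That Section 5.1 leaves the two-dose Arm 3 open to a first-dose cut-off.** It says only "all available safety data up to cut off date defined as 7 days after the dosing", less exact than its own wording for Arm 1, "first 3 subjects up to 7 days after the last dose of the third subject in Dose Arm 1". But the Summary gives the last dose of the respective subject for Arm 3, and the other multi-dose cut-offs (Sections 12.1.9 and 14.7) use the last or final dose. This is a difference in wording, not a second error.
- **That the DMC charter repeats, or fails to correct, the error.** The charter is not available, so neither can be said.

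**Conclusion.** The point holds for one phrase. The Summary's cut-off for the Dose Arm 5 DMC reviews is wrong as written: it names a Dose Arm 4 subject and gives a fixed date that precedes every 20mg/kg dose. Read literally, 0 Arm 5 subjects fall inside it at each of the two to four reviews.

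Severity is minor. The intended rule can be inferred from the surrounding text, and other safeguards limit the harm. It still merits correction, because it is a stated safety-review rule for the highest single dose and neither Section 5.1 nor Section 14.7 puts an explicit correct rule in its place.

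The date order rests on two assumptions, both taken from the protocol: the six Arm 4 subjects reviewed include the third, and Arm 5 dosing starts only after that review. No assumption about recruitment speed is needed.

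**What to change.** In the Dose Arm 5 paragraph of the Summary, define the cut-off as 7 days after the dosing of the respective (third, sixth, ninth, twelfth) subject in Dose Arm 5. Check that the DMC charter says the same.

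Optionally, in the Dose Arm 3 paragraph of Section 5.1, state that the 7 days run from the last dose of the respective subject, to match the Summary. This is harmonisation only. For the single-dose Arms 4 and 5 there is no doubt which dose is meant.

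The cost is one phrase in the Summary, at most one more in Section 5.1, and a check against the charter. Visits, subject numbers, analyses and data collected do not change.
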